Figure 1. IPERGAY Study: Time to first STI (panel a), GC infection (panel b), CT infection (panel c), and syphilis infection (panel d) ¹

begun to prescribe doxycycline PEP to reduce incident STIs in MSM without a confirmatory study or normative guidance. Moreover, the balance of benefits and risks of doxycycline PEP need to be carefully studied in MSM living with HIV as well as in PrEP users in a study powered to assess effectiveness for each population. The relative benefits and risks of doxycycline PEP may differ in MSM living with HIV and PrEP users due to differences in adherence, sexual practices, potential risk compensation, sexual networks, and/or pre-existing antibiotic resistance due to higher prior antibiotic exposure among MSM living with HIV.

In summary, a sufficiently-powered, high-quality study is needed to evaluate the effectiveness of doxycycline PEP in populations both with and without HIV infection, and to evaluate its impact on drug resistance in target bacterial STIs and resident bacterial microbiota. There is a public health need and sufficient clinical equipoise to conduct an effectiveness study of doxycycline PEP as an STI reduction strategy for a diverse population of MSM in the US to address the following key scientific questions: 1) Effectiveness of doxycycline PEP for bacterial STI prevention in MSM and TGW on PrEP, 2) Effectiveness of doxycycline PEP in MSM and TGW living with HIV; 3) Differential tolerability and impact on antimicrobial resistance between MSM/TGW living with HIV and MSM/TGW on PrEP; 4) TCN resistance in GC, CT and syphilis, 5) TCN resistance in commensal Neisseria (which can transfer TCN resistance) and potentially pathogenic Staph Aureus in carriers, and 6) effect on the gut resistome in terms of changes in TCN resistance genes.

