2.2.2.2. Safety, tolerability and acceptability of doxycycline PEP

- Safety: All grade 2 and higher hematologic and hepatic laboratory abnormalities, all grade 3 and 4 adverse events judged to be associated with doxycycline (possibly, probably, or definitely related), and all SAEs.
- Tolerability: in person quarterly assessments of discontinuations of doxycycline, discontinuation of PEP, symptom assessment, and self-reported side effects questionnaire at 6 and 12 months by CASI (computer assisted self-interview),

In person assessment by research staff at scheduled visits to include:

- All permanent doxycycline discontinuation and reasons for discontinuation;
- For all temporary doxycycline interruptions ≥ 7 days, reason for interruption; and
- Side effects:
 - o presence/absence of the following symptoms and if present, whether attributed to doxycycline (if taking) by a) participant and b) investigator: rash, sunburn, headache, change in vision, pain with swallowing, diarrhea, nausea, vomiting, abdominal pain, or other.

CASI questions related to tolerability

- At least once in the past 3 months, I did not take doxycycline within 3 days after sex because I wanted to avoid side effects. (Reported using 5-point Likert scale)
- Were there any other reasons that you did not take doxycycline within 3 days after sex? Yes/No (Y/N) and open-ended response if yes is selected.
- In the past 3 months, do you feel that taking doxycycline affected your sexual experience? (Reported using 3-point scale: negative, neutral, positive effect).

• Acceptability: self-reported acceptability questionnaire by CASI for all doxycycline PEP recipients administered at month 6 and 12.

Answer to the following questions, reported using a 5-point Likert scale, unless otherwise indicated

- Doxycycline is easy to take.
- I'm worried that taking doxycycline will cause antibiotic drug resistance. (reverse coded)
- I'm worried that doxycycline will hurt my body. (reverse coded)
- Taking doxycycline PEP will reduce my condom use. (reverse coded)
- Doxycycline has other good effects for me.
- Taking doxycycline PEP has helped me take my PrEP or ART more regularly.
- A sexual partner has expressed negative feelings about me taking doxycycline. (reverse coded)
- A sexual partner has expressed positive feelings about me taking doxycycline
- Taking doxycycline only when needed after sex and not every day is... (5-point scale from very unacceptable to very acceptable)

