7.5.3. Analyses of the Primary Efficacy Results while on study drug (Per protocol)

For the per-protocol analysis, for each cohort the doxycycline PEP arm will be restricted to study time prior to the first permanent discontinuation of study drug by self-report or documented on the study CRFs.

First discontinuation is defined as first of

- Product discontinuation
- Missed quarterly visit

Descriptive: Occurrence and reasons for first discontinuation will be tabulated (number of participants).

Analysis: The evaluation of the impact of non-disrupted use of doxycycline on any STI will use the same model as specified for the primary analysis, but also potentially adjusted for age, race/ethnicity, baseline STI, and baseline and follow-up sexual risk (number of partners, unprotected anal sex, employment). For the HIV negative cohort, PrEP at baseline; for the HIV positive cohort, viral suppression at baseline will also be considered.

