7.5.5. Analysis of Tetracycline resistance

7.5.5.1. Primary analysis of TCN resistance in GC cases

The primary analysis of TCN resistance in GC will be conducted in the GC positive.

Descriptive statistics: Tabulations of resistance amongst cases (GC: TCN resistance testing missing, not resistant, resistant) will be reported at baseline, month 3, 6, 9, and 12 (and potentially interim visits) in each arm, for any infection site, and broken out by infection site. Additional descriptive information may also be included (i.e. change in MIC in GC cultures amongst those with repeat infections)

Statistical analysis: Assessment of odds of resistance amongst GC cases with resistance results will be assessed by arm using logistic regression with arm as exposure, adjusted for city. To account for repeated infections, repeated measures methods (GEE) will be used. Analysis comparing arms also potentially adjusted for age, race/ethnicity, baseline STI, baseline and follow-up sexual risk (number of partners, unprotected anal sex, employment). For the HIV-negative cohort, PrEP at baseline; for the HIV-positive cohort, viral suppression at baseline will also be considered.

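### The per-protocol STI model and the gonorrhoea resistance model may, at the analyst's option, adjust for sexual risk measured after open-label assignment, which changes what the per-protocol estimate means

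*SAP*

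**What the plan says.** SAP 7.5.3 says the per-protocol evaluation uses the "same model as specified for the primary analysis, but also potentially adjusted for age, race/ethnicity" and then lists "baseline STI, and baseline and follow-up sexual risk (number of partners, unprotected anal sex, employment" as further candidates. The restriction that makes the analysis per-protocol applies to one arm: "the doxycycline PEP arm will be restricted to study time prior to the first permanent discontinuation".

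SAP 7.5.5.1 has parallel wording for gonococcal resistance. The estimand is stated as "Assessment of odds of resistance amongst GC cases with resistance results will be assessed by arm", and the covariate sentence reads "Analysis comparing arms also potentially adjusted for age, race/ethnicity, baseline STI, baseline and follow-up sexual risk".

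Neither section says what would trigger the adjustment, which follow-up visits would supply the values, or which version would be reported as the result.

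The primary analysis (SAP 7.5.1) is intention-to-treat, with site and arm as its only covariates.

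The documents allow that behaviour may respond to the drug. Protocol 1.1 includes "potential risk compensation, sexual networks, and/or pre-existing antibiotic resistance" among the reasons why benefits and risks may differ between the HIV and PrEP cohorts. The acceptability questionnaire (SAP 2.2.2.2) has the item "Taking doxycycline PEP will reduce my condom use".

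**The concern.** Participants know their arm. They are counselled on the earlier effectiveness data (Protocol 2), and recruitment materials describe efficacy (Protocol 4.3). Number of partners and condomless anal sex during follow-up can therefore be consequences of assignment, on the path from doxycycline to infection.

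A regression that holds follow-up behaviour equal across arms removes that path. It estimates the effect of doxycycline at fixed behaviour. SAP 7.5.3 sets out to measure something else, the impact of uninterrupted use, which includes whatever users do differently. Follow-up behaviour also shares unmeasured causes with infection, so conditioning on it can introduce further bias.

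Because the adjustment is optional and ungoverned, the choice between two estimands could be made in an open-label trial after results are seen. The models at stake are a supportive efficacy analysis and an analysis that serves a primary objective (resistance).

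**Working it through.** **1. Design figures used as anchors.** From Protocol 10.2 and SAP 3.3.1: 10% versus 5% quarterly STI prevalence, ICC 0.2, four visits, 370 evaluable at 2:1 (123 control, 246 doxycycline), two-sided 0.05.

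- Repeated-measures factor: (1 + 3 × 0.2)/4 = 0.40.
- Pooled prevalence: (12.3 + 12.3)/369 = 0.0667.
- Null SE: √[0.0667 × 0.9333 × (1/123 + 1/246) × 0.40] = 0.0174.
- Alternative SE: √[(0.09/123 + 0.0475/246) × 0.40] = 0.0192.
- Power: Φ[(0.05 − 1.96 × 0.0174)/0.0192] = 79.5%, against 80% stated.
- Annual risks: 1 − 0.90⁴ = 34.4% and 1 − 0.95⁴ = 18.5%, against 34% and 19% stated.

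The plan's figures reproduce. They belong to the comparison without behavioural covariates and are not in dispute. They supply the relative risk (RR) of 0.50 used below.

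**2. Formula.** Let k be the doxycycline-to-control ratio of follow-up partners, and e the power by which STI risk scales with partners. Then

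total RR = direct RR × kᵉ, and a model that holds partners fixed returns the direct RR = total RR / kᵉ.

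Neither k nor e is in the documents; both are assumptions.

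**3. Direct RR set at 0.50.** The formula is compared with a large simulation (40,000 control and 80,000 doxycycline participants, four quarters, modified Poisson, with and without the log of one plus the partner count).

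| k | e | Total RR, formula | Total RR, simulated | Follow-up-adjusted RR, simulated |
|---|---|---|---|---|
| 0.8 | 0.5 | 0.45 | 0.46 | 0.50 |
| 0.8 | 1.0 | 0.40 | 0.41 | 0.50 |
| 1.0 | either | 0.50 | 0.50 | 0.50 |
| 1.1 | 0.5 | 0.52 | not run | not run |
| 1.2 | 0.5 | 0.55 | 0.54 | 0.50 |
| 1.2 | 1.0 | 0.60 | 0.58 | 0.50 |
| 1.4 | 1.0 | 0.70 | not run | not run |
| 1.5 | 0.5 | 0.61 | 0.60 | 0.50 |
| 1.5 | 1.0 | 0.75 | 0.73 | 0.50 |

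Trial-sized simulations (246:123, 400 per cell, k of 1.1, 1.2 and 1.4) gave total RRs of 0.53, 0.54 and 0.60 for e = 0.5, and 0.57, 0.61 and 0.70 for e = 1.0. These are within about 0.02 of the formula. The adjusted RR was 0.50 to 0.52 throughout.

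For k from 1.1 to 1.4, net effectiveness is 48% (1 − 0.52) down to 30% (1 − 0.70), while the adjusted model reports about 50%. The overstatement is about 2 to 20 percentage points.

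**4. The same relation with total RR held at 0.50.** At k = 0.8, 1.0, 1.2 and 1.5 the adjusted RR is 0.625, 0.50, 0.417 and 0.333 for e = 1, and 0.559, 0.50, 0.456 and 0.408 for e = 0.5. The sign of the error follows the sign of the behaviour change.

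**5. Resistance model.** None of this carries over to SAP 7.5.5.1. Its outcome is resistance given a gonorrhoea case with a result, and that set of cases is itself formed after randomization. The documents offer no basis for signing the effect of adding follow-up behaviour.

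**The case against.** The strongest reply has four parts.

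*The adjustment is only a possibility.* That is correct, and it would be wrong to read the SAP as committing to it. But optionality leaves the analyst to choose the estimand, with no rule for the choice.

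*Nothing shows that behaviour will change.* A reader might infer that the plan overstates effectiveness and that the bias favours the drug. The documents do not support that. Protocol 1.1 reports no difference between arms in self-reported sexual behaviour in the earlier French trial, and a review of presumptive treatment in sex workers without risk compensation. The Protocol's mention of risk compensation concerns differences between the two cohorts, and the condom-use item is asked of doxycycline recipients only. This stands, so the direction must be conditional. It does not close the question: the Protocol itself calls the French sample small (232 men), questions its generalizability, and says event-driven PEP had not been studied in MSM living with HIV.

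*The net effect is already estimated by intention to treat.* This stands, and it limits the point to secondary importance. Protocol 10.2 also plans a related comparison between arms of risk practices and sexual activity.

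*Follow-up behaviour may be needed because only the doxycycline arm loses person-time.* Informative discontinuation is a fair worry. A plain outcome-model covariate that treatment can affect does not solve it; weighting is suited to that job.

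**Conclusion.** The point holds in conditional form and merits a change to the SAP.

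In 7.5.3, optional adjustment for follow-up sexual risk turns the per-protocol estimate into one that excludes effects acting through behaviour. Under assumed partner increases of 10 to 40% and exponents of 0.5 to 1.0, a total RR of about 0.52 to 0.70 would appear as about 0.50. With a partner ratio of 0.8 the error reverses: a total RR of about 0.41 to 0.46 in the simulation would appear as about 0.50. With no behaviour difference there is no shift. These sizes rest on assumptions that the documents neither supply nor contradict, and on partner number standing in for all risk behaviour.

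In 7.5.5.1 the covariate is equally post-randomization, but the direction of bias is unknown. A reader might carry the overstatement of effectiveness across to this model; that does not follow, because it estimates odds of resistance among cases and yields no effectiveness figure.

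The primary intention-to-treat estimate, its test and its power are untouched.

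**What to change.** Delete *and follow-up* from the covariate lists in SAP 7.5.3 and 7.5.5.1, so that sexual risk enters at its baseline value only, and state whether the remaining covariates will be used.

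If the sponsor wants a per-protocol estimate adjusted for follow-up behaviour, label it as a direct effect and show it beside the baseline-adjusted estimate. If follow-up behaviour is wanted to handle informative discontinuation, use it in pre-specified inverse-probability weights for leaving on-drug time and keep it out of the outcome model. Tabulating follow-up partners and condomless sex by arm would let readers judge whether the two estimates should differ.

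The cost is a few words in the SAP and, if chosen, one weight model. Sexual behaviour is already collected in both arms (Protocol 2 and 6.3.7), so no new data are needed. The one statistical downside is that weighting may slightly widen the per-protocol interval.

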7.5.3.1. Study drug use and time on study drug in doxycycline PEP arm

The following descriptive tabulations will be completed for each measure:

- Study drug dispensation (number of participants and number of pills) will be summarized for each study visit over time by cohort.
- Proportion of sex acts and condomless sex acts where doxycycline was taken, based on self-report will be tabulated for each quarter and overall within each cohort. Evaluated for both the mobile app (Blackbook cohort only) and CRF calendar data.
- Semiquantitative assessment (high/low) of concentrations in hair will be tabulated for each quarter and overall within each cohort (Hair cohort only).
- Concomitant use of doxycycline, as documented in the antibiotic use log, will be summarized for the control and doxycycline arms

Descriptive comparisons are planned to evaluate the consistency of measures across different measurement modalities

- Mobile app, hair, and CASI data will be compared using variables defined to approximate the same time period.

7.5.3.2. Assessment of doxycycline in hair

Longitudinal exposure to doxycycline assessed using hair collection.

- A semiquantitative evaluation in the control arm (doxycycline present vs. absent).
- A semiquantitative assessment in the PEP arm (doxycycline concentration high vs. low vs. none).

Descriptive: The proportion of samples with doxycycline present, and the concentration levels will be tabulated for each quarter and overall by study arm within each cohort.

7.5.4. Secondary analysis of efficacy for each site of infection

Secondary endpoints:

- Any GC.
- Any CT.
- Any new early syphilis diagnosis.
- Site of GC infection (pharyngeal GC compared to urine or rectal GC).
- Site of CT infection (pharyngeal CT compared to urine or rectal CT).

Analysis: For secondary endpoints, the same approach as defined for the primary endpoint will be used, restricted to the specific bacterial infections or infection site.

7.5.5. Analysis of Tetracycline resistance

7.5.5.1. Primary analysis of TCN resistance in GC cases

The primary analysis of TCN resistance in GC will be conducted in the GC positive.

Descriptive statistics: Tabulations of resistance amongst cases (GC: TCN resistance testing missing, not resistant, resistant) will be reported at baseline, month 3, 6, 9, and 12 (and potentially interim visits) in each arm, for any infection site, and broken out by infection site. Additional descriptive information may also be included (i.e. change in MIC in GC cultures amongst those with repeat infections)

Statistical analysis: Assessment of odds of resistance amongst GC cases with resistance results will be assessed by arm using logistic regression with arm as exposure, adjusted for city. To account for repeated infections, repeated measures methods (GEE) will be used. Analysis comparing arms also potentially adjusted for age, race/ethnicity, baseline STI, baseline and follow-up sexual risk (number of partners, unprotected anal sex, employment). For the HIV-negative cohort, PrEP at baseline; for the HIV-positive cohort, viral suppression at baseline will also be considered.

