3 OBJECTIVES

3.1 Primary Objectives

- 3.1.1 Evaluate the effectiveness of doxycycline post-exposure prophylaxis (PEP) to reduce STI infections in two populations: a) MSM/TGW living with HIV and b) MSM/TGW taking HIV PrEP.
- 3.1.2 Investigate the impact of doxycycline PEP on development of culture-based tetracycline (TCN) resistance in *N. gonorrheae* and among nasopharyngeal carriers of *S. aureus*

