For resistance we will assess the proportion with tetracycline resistance in visits with *N. gonorrheae* and *S. aureus*. Exploratory endpoints include incidence of tetracycline resistance in *C. trachomatis* and *T. pallidum* using molecular techniques (e.g., CRISPR and CAS-9), for which the molecular technologies are new and the clinical significance of resistance mutations is less clear. Stool samples from 50 participants living with HIV and 50 participants on PrEP will be obtained at baseline, 6 and 12 months for metagenomic evaluation targeting TCN genes. Overall TCN resistance gene abundance (expressed as dpM/patient) and the number of distinct TCN resistance genes present per participant will be assessed at baseline and evaluated for change over time during doxycycline use. Rectal swabs will be collected and stored for future evaluation of shifts in the fecal microbiome, decrease in flora diversity, and quantification of TCN-resistant abundance and diversity

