10.3 Endpoint adjudication

All STI endpoints will be reviewed by a blinded, independent Endpoint Adjudication Committee, following CDC guidelines for the diagnosis of STIs.⁵² Incidence of individual STIs and tetracycline resistance will also be evaluated.

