2.2.1.2. Impact of doxycycline on TCN resistance

1. Resistance of GC to TCN detected in positive GC cultures. Those with positive GC NAAT results will have a swab obtained from the involved anatomic site and other sites of sexual contact in past 90 days (to include throat, rectum, urine) for GC culture-based phenotypic testing. Swabs for GC culture will be collected at time of suspected GC or in patients recalled after positive GC NAAT result reported.
2. Tetracycline resistance detected in *S. aureus* culture-positive nasopharyngeal swabs, collected at baseline, six, and 12 months

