5.2.7. Nasal or oropharyngeal *S. aureus* carrier Population

Participants with nasopharyngeal cultures with *S. Aureus* growth assessed for TCN resistance.

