7.5.5.4. Analysis of TCN resistance in *S. aureus* carriers

The primary analysis of TCN resistance will be conducted in *S. aureus* cases detected at Baseline, 6- and 12-month visits.

Outcome: TCN resistance will be a dichotomous outcome defined as sensitive or resistance, based on e-Test cut-offs.

Descriptive statistics: Tabulations of TCN resistance in *S. aureus* cases (TCN resistance testing missing, not resistant, resistant) will be reported at baseline, 6- and 12-month visits in each arm. (site of *S. aureus*, if found, will not be known).

Statistical analysis: Assessment of difference in prevalence of TCN resistance by arm at each of 6 and 12 months will be assessed by estimating the relative risk of TCN resistance using modified Poisson regression. The model will assess the relative risk of resistance by arm, adjusted for study site at each time point. If an effect is found, assessment of a trend in time will be assessed by fitting a linear trend over study time. If prevalence of resistance is < 5%, analysis will pool across visits.

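### TCN resistance in GC is modelled by arm only among GC cases, so weaker protection against resistant strains could raise the odds ratio with no new resistance; a per-participant estimate with a confidence interval should be read beside it

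*SAP*

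**What the plan says.** Protocol 3.1 sets the second primary objective: "Investigate the impact of doxycycline PEP on development of culture-based tetracycline (TCN) resistance in" *N. gonorrhoeae* and among nasopharyngeal *S. aureus* carriers.

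**Case-only or carrier-only sets**
- SAP 2.2.1.2 defines the GC endpoint as "Resistance of GC to TCN detected in positive GC cultures" and takes the *S. aureus* endpoint from "culture-positive nasopharyngeal swabs, collected at baseline, six, and 12 months".
- SAP 7.5.5.1 gives the GC model: "Assessment of odds of resistance amongst GC cases with resistance results will be assessed by arm using logistic regression". It uses GEE for repeat infections and adjusts for city. The optional covariates include sexual risk during follow-up.
- SAP 7.5.5.4 plans "Assessment of difference in prevalence of TCN resistance by arm at each of 6 and 12 months" by modified Poisson regression, in carriers only. SAP 5.2.7 limits that population to participants with *S. aureus* "growth assessed for TCN resistance".
- Protocol 10.2 agrees: "For resistance we will assess the proportion with tetracycline resistance in visits with" the organism.

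**Nearest text to a randomised denominator**
- SAP 2.2.2.1 and 7.5.4 apply the primary ITT modified Poisson GEE to any GC. This gives an RR for GC, not for resistant GC.
- SAP 7.5.5.1 tabulates GC cases by arm and visit as resistant, not resistant or result missing.
- Protocol 10.3 adds: "Incidence of individual STIs and tetracycline resistance will also be evaluated". It gives no model or denominator.
- Protocol 10.5 (post-closure analyses) compares STI resistance in everyone who received doxycycline with controls before doxycycline, and *S. aureus* resistance with control and with individual baseline. It names no denominator or model.
- Protocol 6.5.1 plans a check for rising MICs, only in participants with repeat GC. In SAP 7.5.5.1 MIC change is optional and descriptive.

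**The concern.** The objective asks what doxycycline does to the development of resistance, which is a causal question about randomised arms. The model answers it in a set that doxycycline itself changes. Protocol 1.1 explains the lack of a GC effect in the French trial by resistant strains, and Protocol 10.2 bases its 35% GC effectiveness on higher US susceptibility. By that reasoning, doxycycline would remove susceptible GC preferentially and leave a higher resistant share among the cases that remain.

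This is selection, a legitimate thing to describe and one that Protocol 1.2.3 raises. The risk is that an OR above 1 is reported as newly developed resistance when it reflects prevention of susceptible infections, possibly while participants in the doxycycline arm have fewer resistant infections each. Protocol 1.2.8 says the resistance data from continued follow-up are meant to inform guidelines. Protocol 1.1 also says that more TCN resistance would not change GC management, so what is at stake is a misread resistance conclusion.

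**Working it through.** **1. Reproduce the plan's GC counts (Protocol 10.2).** Over both cohorts there are 260 control and 520 doxycycline participants, four quarters, 5% GC per quarter, 35% effectiveness and 10% loss.
- Control: 260 × 4 × 0.05 × 0.90 = 46.8, stated as 47.
- Doxycycline: 520 × 4 × 0.05 × 0.65 × 0.90 = 60.8, stated as 61.

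**2. Case-only OR with no new resistance.** Let e = 0.35, let r be the background resistant share (25% to 38%, Protocol 1.2.3), and let k be protection against resistant strains divided by protection against susceptible strains. The documents do not give k, so it is varied.
- Protection against susceptible strains: eS = e / [(1 − r) + r·k]. Against resistant strains: eR = k·eS.
- Case-only OR = (1 − eR) / (1 − eS). Per-participant RR of resistant GC = 1 − eR.
- Example, r = 0.25 and k = 0.5: eS = 0.35/0.875 = 0.40, eR = 0.20, OR = 0.80/0.60 = 1.33, RR = 0.80.

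| k | OR, r = 25% | RR, r = 25% | OR, r = 38% | RR, r = 38% |
|---|---|---|---|---|
| 1 (equal) | 1.00 | 0.65 | 1.00 | 0.65 |
| 0.5 (half) | 1.33 | 0.80 | 1.38 | 0.78 |
| 0 (none; bounding) | 1.88 | 1.00 | 2.30 | 1.00 |

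**3. What the planned outputs already give.** With complete cultures, the RR of resistant GC equals the any-GC RR times the ratio of resistant shares. Half case: 0.65 × 30.8%/25% = 0.80. Bounding case: 0.65 × 38.5%/25% = 1.00. The point estimate can therefore be derived, but without an interval and only if no cultures are missing.

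**4. The RR does not separate prevention from emergence either.** Under equal protection the doxycycline arm has 61 × 0.25 = 15.25 resistant and 45.75 susceptible cases. If 8.2 of the susceptible cases (18%) became resistant, the counts would be about 23.5 and 37.5, against 11.75 and 35.25 in control. That also gives OR 1.88 and RR 1.00.

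**5. Chance of p < 0.05 for the case-only OR with no new resistance** (Wald, r = 25%, clustering ignored).
- Half: SE = √(1/18.8 + 1/42.2 + 1/11.75 + 1/35.25) = 0.436; ln 1.33/0.436 = 0.66; about 10%.
- None: SE = 0.427; ln 1.875/0.427 = 1.47; about 31%.
- At an assumed 50% culture yield: 8% and 18%.
- At 554 enrolled (Protocol 1.2.8), counts × 554/780 with every case cultured: about 9% and 24%.
- At r = 38% and planned size with every case cultured: about 13% and 55%.

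**6. Precision of a per-participant RR at RR = 1.**
- Planned size: 11.75 control and 23.5 doxycycline resistant events; SE(ln RR) = √(1/11.75 + 1/23.5) = 0.357; 95% CI 0.50 to 2.0. Power for a doubling is about 57%.
- 554 enrolled: about 8.3 control events, CI 0.44 to 2.3, power 43%. If half of follow-up in both arms is also lost (assumed): 4.2 events, CI 0.31 to 3.2, power 24%.

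**7. Missing cultures.** Take the bounding case (true RR 1.00) at 50% yield, with odds of resistance in missing versus observed cultures of 2 in one arm and 0.5 in the other. The RR then ranges from 0.62 to 1.56.

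**8. *S. aureus*.** Protocol 1.2.3 gives about 30% carriage. The documents give neither the resistant share among carriers nor any effect of doxycycline on carriage, so nothing can be sized.

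**The case against.** The strongest reply is that most of the companion information is already planned. The any-GC RR uses the ITT model and the resistance tabulation is by arm, and step 3 shows that together they return the per-participant RR. This stands: the gap is an interval, a rule for missing cultures and a caution on interpretation.

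A second reply is that the false-signal risk is modest and smaller at 554 enrolled. This also stands. In the half case the chance is 9% to 10% against a nominal 5%, and the higher figures belong to a bounding assumption.

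A third reply is that the added estimate would be imprecise, that controls chose whether to start doxycycline, and that the SAP (February 2021) predates the closure and was expected to evolve. These points shape the fix but do not remove the need for it.

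Three stronger readings are tempting, and the documents do not support them:
- **The *S. aureus* comparison is shown to be misleading.** The conditioning is the same, but nothing allows its size to be judged, the objective is itself worded among carriers, and Protocol 10.5 adds individual baseline.
- **A per-participant RR above 1 proves emergence.** Prevention alone cannot raise the expected RR above 1 with complete cultures, but step 7 shows that culture loss differing by arm can, and so can chance.
- **The case-only analysis is wrong and should be dropped.** It remains a valid description of selection among cases.

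**Conclusion.** The concern holds as a problem of interpretation for the GC analysis. With 35% overall effectiveness and 25% background resistance, prevention alone gives a case-only OR of 1.33 under half protection against resistant strains and 1.88 under none. Resistant GC per participant is then lower (RR 0.80) or unchanged (RR 1.00). The protocol's own reasoning supports the direction of the strain difference; its size is an assumption, and under equal protection the OR is 1.00. No model in the protocol or SAP estimates resistant GC over all randomised participants with a confidence interval, and none handles missing cultures. The case-only OR and the per-participant RR together say more than either alone, but even the pair cannot fully separate prevention from emergence. The optional adjustment for follow-up sexual risk is a separate, smaller point: it is a post-randomisation variable in an open-label trial.

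**What to change.** Keep the planned analyses and add the following to the SAP, in the combined cohort.

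1. Model TCN-resistant GC (yes/no) per participant-quarter among all randomised participants tested, counting no GC as 0, with the primary modified Poisson GEE (arm and site).
2. Use follow-up to 5/13/2022 in both arms as the main comparison. As a sensitivity analysis, censor control time at the doxycycline start date recorded under Protocol 6.3.24. That start is voluntary, so censoring there may be informative.
3. Report by arm the GC-positive quarters without a culture result, with a simple sensitivity analysis, for example varying the odds of resistance in missing versus observed cultures from 0.5 to 2 in opposite directions by arm.
4. Present this RR beside the case-only OR and the any-GC RR. State that an OR above 1 is not proof of new resistance, that a null RR is not proof of none, and that an RR above 1 suggests emergence or greater exposure only if culture loss by arm and chance are excluded.
5. Optionally, describe resistant *S. aureus* carriage among all participants swabbed, counting non-carriers as 0.
6. Remove follow-up sexual risk from the optional covariates in SAP 7.5.5.1.

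The cost is SAP wording and one added model, on data already planned for collection; SAP section 1 allows such revision. The price is low precision: about 12 resistant control events at planned size and about 8 or fewer at 554 enrolled, fewer still once follow-up is cut at 5/13/2022.
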